11.1 Evaluation and Reporting of Adverse Events

All AEs (i.e., a new event or an exacerbation of a pre-existing condition) that occur from the time informed consent is signed and up to 30 days after the study drug has been discontinued must be recorded as an AE on the AE eCRF. The Investigator must follow all AEs until the AE resolves, or until the Investigator and/or the Medical Monitor determine the event is chronic or clinically stable. If an AE remains unresolved at the conclusion of the study, the Investigator and Medical Monitor will make a clinical assessment to determine whether continued follow-up of the AE is warranted. All participants who have received at least one exposure to study therapy will be evaluated for safety of study treatment.

The Investigator should attempt to establish a diagnosis of the event based on signs, symptoms and/or other clinical information. In such cases, the diagnosis should be documented as the AE and not the individual signs/symptoms.

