11.2 Assessment of Adverse Events

All AEs must be promptly documented on the Adverse Event eCRF and assessed by the Investigator. Details of the event must include the dates of onset and resolution, severity,

relationship to study drug, seriousness, and whether the event caused the participant to withdraw from the study, outcome and timing with regard to administration of the study drug.

Severity: Severity should be graded and recorded according to the table below.

Severity	Definition	
Mild	Awareness of event but easily tolerated	
Moderate	Discomfort enough to cause interference with usual activity	
Severe	Inability to carry out usual activity, incapacitating, requires medical intervention	

Relationship: The relationship of the Adverse Event to the study drug will be determined by the Principal Investigator, and assessed using the following definitions:

Relatedness	Description
Not Related	There is no evidence of a causal relationship and a causal relationship cannot be reasonably attributed to the study treatment or procedures. The event is clearly due to extraneous causes.
Unlikely Related	A poor temporal relationship exists between the event onset and administration of intervention. The event could easily be explained by the participant's clinical state, intercurrent illness, or concomitant therapies.
Possibly Related	A relationship cannot be ruled out with certainty and the event may be related. There is some evidence to suggest a causal relationship but the influence of other factors may have contributed to the event, such as the participant's clinical condition or concomitant treatment.
Probably Related	The event is likely related to the intervention. There is evidence to suggest a causal relationship, such as reasonable temporal sequence from treatment administration or procedure. The influence of other factors is unlikely.
Definitely Related	The event is clearly related to the intervention. There is clear evidence to suggest a causal relationship. The influence of other factors can be ruled out.

These criteria, in addition to good clinical judgment, should be used as a guide for determining the causal assessment. If it is felt that the event is not related to study drug therapy, then an alternative explanation should be provided.

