Facsimile (fax) number for SAE report forms, to be sent within 24 hours after awareness of the event:

North America: PPD

The Site Investigator, or designated staff, is also responsible for entering the SAE information in the ADCS Electronic Data Capture (EDC) system (i.e., event term, start stop dates, causality, and severity) according to study-specific eCRF Completion Guidelines. The ADCS Medical Monitor and ADCS Project Director will be automatically notified via email upon entry of an SAE into the ADCS EDC system. A member of the ADCS Medical Safety team will inform the DSMB of the occurrence of any SAEs within 7 days of being reported. The DSMB may at any time request additional information from the ADCS in relation to a reported event.

If only limited information is initially available, follow-up reports are required. If an ongoing SAE changes in its intensity or relationship to study drug or if new information becomes available, a follow-up SAE report should be sent to within 24 hours of the Investigator becoming aware of the updated information using the same procedure used for the transmission of the initial SAE and the same event term should be used. In addition, new or revised event information must be entered into the ADCS EDC at the same time.

All SAEs should be followed to resolution or stabilization. For any questions relating to SAEs, please contact the ADCS Medical Monitor via telephone or email at the number listed on the protocol face page.

Suspected Unexpected Serious Adverse Reactions

Suspected unexpected serious adverse reactions (SUSARs) are serious adverse events that are not listed in the Investigator's Brochure as an expected AE and that the Investigator assesses as possibly related or probably related or definitely related to study drug or study procedure. United States 21 CFR 312.32 and European Union Clinical Trial Directive 2001/20/EC and the associated detailed guidance or national regulatory requirements in participating countries require the reporting of SUSARs to regulatory authorities. As the clinical trial sponsor, Biohaven is responsible for, and has procedures consistent with regulations that will be followed for, expedited reporting of SUSARs.

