• On-Treatment in Study (Safety Assessments): except where indicated, "on-treatment" for any Troriluzole treatment (combined Randomization Phase and Extension Phase) will include all assessments after first day of Troriluzole and up to the last day of Troriluzole treatment + 30 days. For AE summaries for any Troriluzole treatment (combined Randomization Phase and Extension Phase), On-treatment (Troriluzole) will include AEs with start date on or after first day of dosing with Troriluzole up to last day of dosing with Troriluzole + 30 days.

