#### 4.10.2 Adverse Events

AEs will be coded using MedDRA and displayed in tables and listings by system organ class (SOC) and preferred term (PT).

Analyses of AEs will be performed for those events that are considered treatment-emergent (TEAE), where treatment-emergent is defined as events that first occurred or worsened on or after first dose of study medication. See section 4.4 for the detailed definition of "on-treatment" treatment-emergent AEs (TEAEs) and see section 4.3.7 for additional details when onset date is partial.

The number and percentage of participants with the following AEs will be summarized by treatment group and overall for the Randomization and Extension Phases, separately, as well as just overall for subjects after at least one dose of BHV-4157 in any phase.

- TEAEs
- TEAEs Related, Probably Related or Possibly Related to Treatment (An AE is considered to be related to study drug if the relationship is either definitely, probably or possibly related.)
- Treatment-emergent SAEs
- TEAEs leading to discontinuation of study treatment
- TEAEs by highest severity (mild, moderate, severe)
- TEAEs Related, Probably Related or Possibly Related to Treatment by highest severity (mild, moderate, severe)
- TEAEs indicating potential Interstitial Lung Disease (using Standardized MedDRA Queries (SMQ) Interstitial Lung Disease including Eosinphilic Pneumonia and Hypersensitivity Pneumonitis)

In the above tabulations, each participant will contribute only once for a given preferred term (i.e., the most related occurrence or the most severe occurrence) to each of the incidence rates in the descriptive analysis, regardless of the number of episodes. No formal hypothesis-testing analysis of AEs incidence rates will be performed.

All AEs occurring pre-treatment, during the Randomization and Open Label Extension Phases, and throughout the entire study will be listed. Additional listings will be provided including all deaths, SAEs, and AEs leading to withdrawal of study drug.

Listings will indicate whether subject was active during COVID-19 pandemic crisis and the date of first visit impacted.

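### The pooled any-BHV-4157 adverse-event tables select events by start date only, so a placebo-phase event that worsens or becomes serious on open-label drug is left out if it stays on its original record

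*SAP*

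**What the plan says.** SAP 4.10.2 gives the general rule: "treatment-emergent is defined as events that first occurred or worsened on or after first dose of study medication". It refers the reader to 4.4 for the detailed on-treatment definition. It plans the same tabulations for each phase separately and also "just overall for subjects after at least one dose of BHV-4157 in any phase".

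For that pooled summary, SAP 4.4 states: "On-treatment (Troriluzole) will include AEs with start date on or after first day of dosing with Troriluzole", with the window closing 30 days after the last dose. The rule does not mention worsening or seriousness.

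Protocol 11 defines a TEAE as one that develops, worsens or becomes serious after the first dose. Protocol 12.7.3 also counts events that intensify.

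SAP 3.1 makes everyone dosed with BHV-4157 in either phase the primary population for safety summaries of all exposure. Placebo participants who enter the open-label extension therefore belong to it.

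**The concern.** Placebo participants can move straight from the Week 48 visit into open-label treatment (Protocol 2 and 8.1.12), carrying ongoing AEs with them. If one of those AEs becomes worse or serious on BHV-4157, the TEAE definitions treat that change as emergent. The pooled rule looks only at when the AE began, which was before the first BHV-4157 dose, and leaves it out.

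At stake is the completeness of the SAP's main description of safety under any BHV-4157 exposure, including its SAE and highest-severity rows. A selection rule that works in one direction is undesirable there, even in descriptive tables.

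**Working it through.** The plan gives no figure to reproduce. The check compares the rules on test cases for an original placebo participant.

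**Anchor.** SAP 4.10.2 and Protocol 11 count from the first dose of study medication, which for this participant is placebo. The pooled table needs a rule counted from the first BHV-4157 dose, and only SAP 4.4 supplies one. The middle column below applies the TEAE definitions from that later anchor.

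| Case | TEAE definitions, from first BHV-4157 dose | SAP 4.4 pooled rule |
|---|---|---|
| AE starts on open-label drug | Counts | Counts |
| Placebo-phase AE worsens on open-label drug, entered as a new record | Counts | Counts |
| Placebo-phase AE worsens on open-label drug, original record kept | Counts | Omitted |
| Placebo-phase AE becomes serious on open-label drug, original record kept | Counts under Protocol 11 | Omitted |
| Placebo-phase AE, unchanged | Does not count | Does not count |

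The rules differ in the third and fourth cases only.

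**Can an original record be kept?** Protocol 11.1 requires recording of "a new event or an exacerbation of a pre-existing condition", but does not say that worsening of an AE already on record needs a second record. For SAEs, Protocol 11.3 points towards keeping the event: "If an ongoing SAE changes in its intensity or relationship to study drug or if new information becomes available, a follow-up SAE report" is to be sent, under the same event term.

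**Does another rule rescue the case?** The worst-case rule in SAP 4.3.7 mentions worsening, but applies only when the start date is partly or wholly missing. Here the start date is known.

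**Direction.** AEs that start on drug are a subset of AEs that start, worsen or become serious on drug. The start-date rule can therefore lower a pooled count but never raise it.

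**Which rows lose.** Within a table, "each participant will contribute only once for a given preferred term". A participant with another on-drug TEAE still counts in the any-TEAE row, so the loss falls on particular preferred terms, seriousness or severity.

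**Scale of one omission.** Inputs: 168 participants per arm and at most 26% dropout (Protocol 12.1.1). Assumptions: all 168 active-arm participants are dosed, and switchers number 168 (no dropout, all enter), 168 × 0.74 ≈ 124 (all completers enter) or 124 × 0.5 = 62 (half enter).

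- 168 + 168 = 336 exposed; switchers 168/336 = 50.0%; one participant is 1/336 = 0.30 points.
- 168 + 124 = 292 exposed; switchers 124/292 = 42.5%; one participant is 1/292 = 0.34 points.
- 168 + 62 = 230 exposed; switchers 62/230 = 27.0%; one participant is 1/230 = 0.43 points.

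These figures show what one omission does. They do not say how many there would be.

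**The case against.** The strongest reply is that the omission depends on how sites record worsening. Read naturally, Protocol 11.1 could lead a site to open a new entry with its own onset date, which the start-date rule then counts. The eCRF completion guidelines mentioned in Protocol 11.3 might settle this, but they are not among the documents reviewed. This stands as a limit on size. It does not remove the conflict between the rules, because nothing in the protocol or SAP requires the new entry.

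A second reply is that start date is nearly all the data allow. Protocol 11.2 says "Details of the event must include the dates of onset and resolution, severity" and other items, but names no date of worsening. This largely stands for non-serious worsening kept on one record. It does not cover AEs that become serious or worsen as SAEs, where SAE reports and follow-ups can date the change.

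Third, existing safeguards limit the harm. All AEs are listed, with separate listings for deaths, SAEs and AEs leading to withdrawal. SAP 4.10.9 requires narratives for on-treatment SAEs and for discontinuations due to AEs. This stands.

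A reader might infer more than the documents support:

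- *That the between-arm safety comparison is biased.* It is not. The rule governs only the pooled summary, and "No formal hypothesis-testing analysis of AEs incidence rates will be performed".
- *That a definite percentage of events is lost.* No document gives a rate for placebo-phase AEs that persist to entry, worsen on drug and stay on one record.
- *That the Extension Phase table certainly counts what the pooled table drops.* SAP 4.4 sets no start-date condition for that phase, so it may. But the sentence does not say what must fall inside the window, and an undated change is as hard to place there.
- *That AEs from before any study drug are lost in the same way.* Protocol 8.1.2 puts those in medical history, so they are a lesser case.

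**Conclusion.** The pooled rule in SAP 4.4 is wrong as written. It conflicts with the TEAE definition in SAP 4.10.2 and with Protocol 11, and it can make the pooled TEAE, SAE and severity counts too low. The conclusion is conditional on the AE staying on its original record. The number of affected events is unknown and probably small, because an AE must start before the first BHV-4157 dose, still be ongoing at entry, and then worsen or become serious on drug. The mismatch in wording is certain; the undercount is possible, not shown. Efficacy and the double-blind safety comparison are untouched. The correction is worth making because it is cheap and the rule errs in one direction only.

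**What to change.** In SAP 4.4, change the rule for the pooled any-BHV-4157 summaries to admit AEs that start, worsen in severity or become serious from the first BHV-4157 dose to 30 days after the last. Add two operating rules:

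- Date the change from SAE and follow-up SAE data where available.
- Where an AE is known to have worsened or become serious but the date of change is unavailable, count it as treatment-emergent. This borrows the worst-case principle of SAP 4.3.7 by analogy, since that section covers missing start dates only.

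The cost is one SAP sentence with these rules, one derivation, and some reconciliation of SAE report data with the EDC, since Protocol 11.3 has SAE forms sent separately by fax. Undated changes may cause a slight overcount. New records for an exacerbation already count, so the gain is mainly in AEs that became serious or worsened as SAEs, plus known but undated changes. Non-serious worsening that leaves no trace beyond the original record stays undetectable; finding it would need a date-of-change field, which is new data collection and not proposed here. No protocol amendment is needed. SAP 4.5.2 keeps extension data out of the primary analysis, so the change does not touch it.

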#### 4.5 Planned Analyses

DSMB analyses of safety data will be performed quarterly throughout the trial period by an unblinded safety ADCS biostatistician who is not involved in the final study analysis. The quarterly analyses include an Executive Summary and a Study Summary (extracted from the protocol). These summaries are followed by tables and figures detailing elements of the current data base related to safety, specifically: Screening and Enrollment, Enrollment by MMSE, Enrollment by Month, Enrollment by Site, Inclusion and Exclusion, Screen Failure by Inclusion Criteria, Screen Failure by Exclusion Criteria, Early Discontinuation, Protocol Deviations, Demographics and Baseline Outcomes, Vital Signs, Safety, Adverse Events with Onset Prior to Randomization, Adverse Events with Onset Following Randomization, Adverse Events by Severity, AE by relatedness, Adverse Events summarized by MedDRA SOC–PT, Serious Adverse Events, and Safety Labs.

#### 4.5.2 Primary Analysis After Double-blind Randomization Phase and Final Analysis After OL Extension Phase

The primary efficacy (including the primary, secondary and exploratory endpoints of the Randomization Phase) and safety analysis will be conducted after the last subject completes their Week 48 visit, or discontinues from the Randomization Phase. The study will be unblinded and the primary analyses will include all data from the double-blind Randomization Phase of the study, but will not include summaries of efficacy and safety data accumulated from the Extension Phase.

Interim looks at data from the Extension Phase may be performed after the completion and unblinding of the Randomization Phase, particularly for safety purposes.

A final analysis of the Open Label Extension Phase data will be completed after the last subject completes their last study visit. This will summarize for descriptive purposes all efficacy data collected in the open-label Extension Phase as well as all safety, laboratory, and other data collect though the entire study. Change from baseline will be based on the Extension Phase Baseline, unless otherwise specified.

Additional analyses may be conducted during the open label Extension Phase of the study to support regulatory and administrative requirements.

#### 4.6 **Participant Disposition**

A summary of participant disposition will be tabulated for all participants by treatment group and overall, including:

- Number of participants enrolled and signed informed consent form
- Number of enrolled participants excluded from the study prior to randomization and reason for exclusion
- Number of participants randomized
- Number of participants treated in Randomization Phase
- Number of mITT participants in Randomization Phase
- Number of participants who completed the Randomization Phase
- Number of participants who prematurely withdrew from the Randomization Phase and reasons for withdrawal
- Number of subjects who entered the Extension Phase
- Number of subjects treated in Extension Phase
- Number of mITT subjects in Extension Phase
- Number of subjects who completed the Extension Phase
- Number of subjects who withdrew from the Extension Phase and reasons for withdrawal

A special form will collect information on whether a visit was impacted by the COVID-19 pandemic crisis and will be used for all visits on or after March 1, 2020. This form will collect the specific impact on the visit (i.e. missed visit, in-person visit not all assessments completed, in-person visit occurring earlier or delayed, remote visit video, and remote visit telephone) as well as how COVID-19 impacted on a given visit (i.e. subject diagnosed/quarantined, site closure/restricted access, subject unwilling/unable to come to site, other). If the subject is terminating the study prematurely the CRF will also collect whether the reason was related to COVID-19 (yes or no).

An additional summary will present the disposition of subjects whose discontinuation was indicated as being related to the COVID-19 pandemic crisis on the COVID-19 CRF.

For the randomized subjects active during COVID-19, the impact of the COVID-19 pandemic crisis on the study will be summarized by presenting (by treatment and overall):

- number and percentage of randomized subjects active in the double-blind phase during the pandemic crisis, as referenced by having at least one visit in the double-blind phase on after the March 13, 2020 National Emergency declaration
- number and percentage of randomized subjects reporting (on the CRF) at least one impact on a given visit (missed visit, in-person visit not all assessments completed, in-person visit occurring earlier or delayed, remote visit video, and remote visit telephone) a subjected will be included in each category they reported in the period
  - Summarize at any time in double-blind phase
  - Summarize by week (analysis window)
- number and percentage of randomized subjects reporting (on the CRF) how COVID-19 impacted on a given visit (diagnosed/quarantined, site closure/restricted access, subject unwilling/unable to come to site, other) a subjected will be included in each category they reported in the period
  - o Summarize at any time in double-blind phase
  - Summarize by study week (analysis window)
- Time of first visit impacted by COVID-19 pandemic crisis (based on the first visit date indicated as impacted from the COVID-19 CRF)
- Duration of time in double-bind phase impacted by COVID-19 pandemic crisis (duration = date of last visit impacted date of first visit impacted + 1) (based on the first visit date indicated as impacted from the COVID-19 CRF)

A by-subject listing of study completion information for both the Randomization and Extension Phases, including the reason for withdrawal and impact due to COVID-19, if applicable, will be presented.

A listing of all subjects with at least one visit impacted by COVID-19 pandemic crisis with the impact and how the impact was related to COVID-19.

#### 4.7 Demographic and Baseline Characteristics

Tabulations of demographic and baseline characteristics, including age, sex, racial group, smoking habits, level of education, disease and medical history, and current standard of care treatment, will be made for all treated participants. A separate set of tabulations will be made for participants enrolled but not randomized. Demographic information will be summarized by treatment group and for all treatment groups combined.

In addition to all Treated subjects additional summaries will be provided for:

- Subjects completing or discontinuing the double-blind randomization phase before March 13, 2020 (the reference date for the start of the COVID-19 pandemic based on the date National Emergency declared)
- Subjects still active in the double-blind randomization phase on or after March 13, 2020

Demographic and other baseline data will also be provided in by-participant data listings.

#### 4.8 Efficacy Evaluation

Unless otherwise noted, all efficacy analyses will be conducted using all available in-clinic assessments from the mITT population during the double blind phase. Remote assessments during the double blind phase will be included in sensitivity analyses. All efficacy data will be included in listings by participant, treatment group, visit and phase (as applicable).

